- Our primary objective is to assess the efficacy of a long- acting antihistamine, Cetirizine, on opioid- induced pruritus in a double-blind, placebo controlled study. The primary outcome will be number of treatment failures between the treatment and placebo groups. Treatment failure is defined as persistent itch score of > 3 3hrs after receiving the intervention.
- 2. Our secondary objectives are to analyze:
 - The correlation between baseline serum tryptase levels and the occurrence of opioid- induced pruritus.
 - The effect of age, race, sex on opioid induced pruritus and the influence of these parameters on antipruritic effect of the drug.

Methods:

Subject recruitment:

This study is a randomized, double blind placebo controlled study. Subjects 6-18yrs of age, requiring treatment with oral or intravenous opioids will be recruited from the pediatric inpatient units at Children's Hospital of Richmond at VCU.

Inclusion criteria:

- Children age 6-18yrs on opioids who develop pruritus and are willing to participate in the study

Exclusion criterias:

- Children with history of chronic urticaria
- Children with other chronic pruritic condition like eczema, contact dermatitis, psoriasis
- Children with known hypersensitivity to cetirizine/zyrtec
- Children on second generation antihistamine 1 week prior to the study recruitment
- Children who are unwilling or unable to swallow the capsule.
- Children with chronic liver or kidney disease

Study Design:

After obtaining an informed consent from the parent or guardian, and an informed assent from children ages 12 years and above, serum tryptase levels will be drawn at baseline. For subjects whose baseline tryptase could not be drawn prior to the onset of itch symptom, a second attempt will be made either 24hrs after being symptom free or at a later date either in the inpatient or outpatient setting when they are free of symptoms.

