Subjects who develop pruritus will have a baseline itch score measured at the onset of the itch symptom. Subjects with itch score of ≥ 3 will be randomized in a double blind fashion to the treatment group with cetirizine 10 mg once daily or to the placebo group. A tryptase level will be obtained 15-60 minutes after the onset of itching. Subjects will have itch scores measured at two time points from receiving the intervention, one at 3hours and other at 12 hours. Subjects will be allowed to receive rescue Diphenhydramine (Benadryl) 3 hours post intervention at the discretion of the treating physician.

Treatment failure is defined as an itch score of ≥3 at 3 hours post intervention and will result in discontinuation from the study. Successfully treated subjects will have a second itch score measured at 12 hours post intervention to analyze the persistence of antipruritic effect of the intervention. The numbers of treatment failures in each group are recorded. The total number of rescue Benadryl doses in each group will also be

recorded. The opioid dose, interval and total doses that each subject receives will be recorded. Patients whose treatment has been successful in controlling the pruritus (itch score ≤ 2) will continue in that arm for a maximum of 12 hours or till discharge whichever is earlier. Patients may drop out of the study at any time. The reason for dropping out will be recorded. At the conclusion of the study, patients will be reassessed by the primary team for further need for any anti-pruritic medications.

Primary Outcome

Number of treatment failures in the study group versus the placebo group at 3 hours post randomization

Secondary Outcomes:

- 1. Number of drop outs in the study group versus the placebo group at the end of the study period.
- 2. Tryptase levels (Total and mature) in subjects who develop opioid-induced pruritus versus those who do not.
- 3. Change in Tryptase levels (Total and mature) from baseline in subjects who develop pruritus
- 4. Effect of age, race, and sex on the incidence of opioid-induced pruritus
- 5. Effect of age, race, and sex on response to cetirizine in subjects with opioid-induced pruritus.
- 6. Change in the baseline itch score between treatment and the placebo group.
- 7. Number of rescue Benadryl doses between treatment and the placebo group.

Preliminary Results:

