Based on our experience (n=16) over the last few months, 37% (n=6) of patients treated with opioids in the inpatient setting develop pruritus. Of those 6 patients, 66.6% were successfully treated with an antihistamine and were able to continue treatment on the same opioid.

Statistical Method:

Data will be analyzed using Chi square, student t-tests and Mann-Whitney U test (for non-parametric data) where appropriate. A p value of <0.05 will be considered significant.

Assuming a 50% reduction in the failure rate to be clinically significant, a sample size of 66 confers a power of 0.8 at α =0.05. Assuming a 10% drop out rate in each group a total of 73 patients will be recruited.

Time line:

We plan to recruit at least 1 patient per week for this study. The study should be completed in 2years. There is a real chance of completing this study much earlier than the 2 year time frame.

Investigator responsibilities:

- The study will be approved by the Western Institutional Review Board
- Conduct the study smoothly and effectively
- Report any adverse effects to McNeil Pharmaceuticals.
- At the completion of the study the data will be presented to McNeil before sending in for publication.

Future research direction:

- 1. To analyze the effect of antihistamine on opioid-induced itching in a much larger sample size.
- 2. To investigate titration prick skin testing to opioid as a predictor of opioid-induced itching.

Limitation of the study:

1. Itch scale is subjective and hence there is no objective way to assess improvement in itching

Sample size calculation

Sample sizes for an α = 0.05 significance level with a two group continuity corrected χ 2 test of equal proportions – 1 sided test, equal sample sizes in each group

Placebo Group	Treatment Reduction	Treatment Group	Sample Size Per Group 80% Power	Sample Size Per Group 90% Power
0.3704	10% Reduction	0.3333	2,102	2,890
0.3922	15% Reduction	0.3333	857	1,174
0.4167	20% Reduction	0.3333	440	599
0.4444	25% Reduction	0.3333	255	346
0.4762	30% Reduction	0.3333	159	214
0.5556	40% Reduction	0.3333	70	90
0.6667	50% Reduction	0.3333	33	43
0.8333	60% Reduction	0.3333	15	19

ITCH SCORE

	1=No		3= Moderate	4= Severe pruritus
	pruritus	(no intervention	pruritus	
		necessary)	(intervention	
			necessary)	
3hrs				
12hrs				

Description of the scores:

- 1. No pruritus- absence of any itching

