- 2. Mild pruritus- presence of itching in only one location of the body (e.g. faces or arm). No intervention necessary as assessed by the investigator and the patient agreeing to the decision. Usually the itching is not relieved by the patient and only reported after being prompted by the investigator/
- 3. Moderate pruritus- presence of itching in more than one location, typical in 2 locations (e.g. arms and thorax). Intervention necessary as assessed by the investigator and the patient.
- 4. Severe pruritus- severe itching which involves almost the entire body and often disturbing the patient.

Score of \geq 3-included in the randomization

Improvement is a score of ≤ 2 at 3hrs

References:

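### Secondary outcome 6 is left to an unadjusted t-test or Mann-Whitney test; stratifying the 3-hour itch score by entry score (3 or 4) would be a free, modest gain in power

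*Combined protocol and SAP*

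**What the plan says.** - **Outcome.** Secondary Outcomes, item 6, reads in full: "Change in the baseline itch score between treatment and the placebo group". It does not say how change is computed, at which time, or with which test.
- **Tests.** Statistical Method says: "Data will be analyzed using Chi square, student t-tests and Mann-Whitney U test (for non-parametric data) where appropriate". No test is assigned to item 6, and no stratified or covariate-adjusted analysis appears anywhere.
- **Entry score.** Study Design has a baseline score taken when itching starts, and then: "Subjects with itch score of ≥ 3 will be randomized in a double blind fashion". On a scale of 1 to 4, entry is therefore 3 or 4.
- **Follow-up scores.** Study Design schedules scores at 3 and 12 hours, but the 12-hour score only for children treated successfully at 3 hours.
- **Cut-off.** Study Design: "Treatment failure is defined as an itch score of ≥3 at 3 hours post intervention". Description of the scores agrees: "Improvement is a score of ≤ 2 at 3hrs". Specific aims differs: "Treatment failure is defined as persistent itch score of > 3 3hrs after receiving the intervention".

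**The concern.** Item 6 is the only outcome that uses the whole itch scale, so it could show shifts that the failure/success split discards. Entry score takes just two values, is known before treatment, and enters any change score directly. An unadjusted test on change gives entry score a fixed weight whether or not that weight suits the data. If entry score says little about the 3-hour score, subtracting it adds noise. The plan has the information to avoid this and does not use it.

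The time point matters too. A comparison at 12 hours would be confined to children selected on their 3-hour result, so the arms would no longer be compared as randomised.

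At stake is some precision, and a clear definition, for one secondary outcome.

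**Working it through.** **1. The plan's own figure.** None is stated for item 6. The trial size comes from Sample size calculation: failure 0.6667 v 0.3333, one-sided 0.05, 80% power, continuity-corrected.

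- Uncorrected: n = [1.645·√(2·0.5·0.5) + 0.8416·√(0.6667·0.3333 + 0.3333·0.6667)]² / 0.3334² = (1.1631 + 0.5611)² / 0.11116 = 26.75.
- Corrected: (26.75/4)·[1 + √(1 + 4/(26.75·0.3334))]² = 6.6875·(2.2036)² = 32.5, so 33 per group and 66 in all, as printed.

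The design effect as a log odds ratio is ln[(0.6667/0.3333)/(0.3333/0.6667)] = ln 4 = 1.386.

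**2. Where a gain can come from.** Let B be entry score, Y the 3-hour score, D = Y − B, and β the slope of Y on B within arm. The variance that D carries beyond what adjustment for B would leave is (1 − β)²·Var(B). If a share p enters at 4, Var(B) = p(1 − p): 0.21 at p = 0.3 and 0.25 at p = 0.5. The excess is greatest at β = 0 within the range 0 to 1, vanishes at β = 1, and returns above 1.

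**3. Subtraction itself is not the cause.** Within the stratum B = 3, D = Y − 3; within B = 4, D = Y − 4. Subtracting a constant leaves ranks unchanged, so a Wilcoxon test stratified by entry score (van Elteren) gives the same result on D as on Y. Simulated power was identical in every setting where both were run.

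**4. Size of the gain.** Simulated trials had 33 per arm, a cumulative-logit model, placebo failure 2/3, treatment log-odds 1.386, and two-sided 0.05. The table takes 30% to 50% entering at 4 and combines two simulations (4,000 and 2,000 trials per setting) with different assumed cut-points.

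| Assumed log-odds of entry 4 v 3 | t-test on change | Mann-Whitney on change | Stratified Wilcoxon, 3-hour score |
|---|---|---|---|
| 0 | 0.79–0.82 | 0.79–0.82 | 0.86–0.87 |
| 0.5 | 0.82–0.83 | 0.82–0.83 | 0.85–0.86 |
| 1 to 2 | 0.84–0.86 | 0.84–0.86 | 0.84–0.86 |

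A further run over entry log-odds 0 to 3 gave 0.77 to 0.85 on change against 0.82 to 0.87 stratified, a gain of about 0 to 8 points. As step 2 predicts, the gain is largest at 0, near zero at 1 to 2, and opens again at stronger relations (3 to 4). Type I error was near 0.05 (0.04 to 0.065) for all three tests in the run where it was tabulated.

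**5. What stratifying does not do.** Two constructed trials, each with 33 per arm and 16 entering at 4 in each arm, counting failure as 3 or above:

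- *Equal failures, 22 v 22.* Treatment: 11 go 3→2, 6 stay at 3, 16 go 4→3. Placebo: the same, except that the 16 stay at 4. Mean change is (−11 − 16)/33 = −0.82 v −11/33 = −0.33. The t-test on change gives p < 0.001; the stratified test gives p = 0.00007.
- *Failures 11 v 22, favouring treatment (p = 0.014).* Treatment: 17 go 3→2, 5 go 4→2, 11 stay at 4. Placebo: 11 go 3→1, 6 stay at 3, 16 go 4→3. Mean change is (−17 − 10)/33 = −0.82 v (−22 − 16)/33 = −1.15, favouring placebo. The t-test on change gives p = 0.057; the stratified test also favours placebo, at p = 0.011.

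These show what is possible, not what is likely.

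**The case against.** The strongest objection is that little is wrong. Item 6 is secondary and has no power claim. Nothing in the text says levels are subtracted or averaged; a shift table would also count as change. With balanced entry scores, the arm difference in mean change equals the arm difference in mean 3-hour score. The gain rests on a relation the documents do not report. All of this stands, and it limits the point to a recommended improvement. It does not remove the point, because neither listed test for a score uses entry score, and adjusting costs nothing.

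A reader might infer three stronger things. The documents support none of them.

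- *That a change score is invalid because 4→3 and 3→2 both count as −1 although only the second reaches success.* The tie is real under simple subtraction, but step 3 shows that subtraction is harmless once entry score is a stratum. Moreover, 4→3 is a failure under Study Design and Description of the scores but not under Specific aims.
- *That the proposed analysis would keep item 6 in line with the primary outcome.* Step 5 shows that it can disagree too, sometimes more sharply. Disagreement with a two-category primary outcome is not an error; a four-level outcome is meant to show what the split hides.
- *That it cures the ceiling.* A child entering at 4 cannot score higher at 3 hours, whichever variable is analysed.

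**Conclusion.** The point holds as a modest, free improvement. As written, item 6 has no stated calculation, time point or test, and the tests available to it ignore entry score. Stratifying or adjusting is worth about 0 to 8 points of power at 33 per arm over entry log-odds of 0 to 3, with no material loss. This assumes the design failure rates, a cumulative-logit model, 30% to 50% entering at 4 in the tabulated settings, and an entry-to-3-hour relation that the documents do not give. The primary outcome, sample size and significance level do not depend on it. The conflict between the failure definitions in Specific aims and Study Design is separate and must be reconciled; the proposed analysis of item 6 uses all four levels and does not depend on the cut-off.

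**What to change.** - In Secondary Outcomes, redefine item 6 as the 3-hour itch score on its four levels, compared between arms. Name 3 hours because 12-hour scores are planned only for 3-hour successes.
- In Statistical Method, name one analysis: a Wilcoxon test stratified by entry score 3 or 4 (van Elteren), or a proportional-odds model with entry score as covariate.
- Report the entry-by-3-hour score table for each arm, so that every transition can be seen.
- Reconcile the failure definitions in Specific aims, Study Design and Description of the scores.

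The cost is one sentence in the outcomes list, one in Statistical Method, and a small table in the report. No new data are needed, because the entry and 3-hour scores are already scheduled.

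### The plan's only significance rule, p<0.05, also covers seven secondary outcomes, with no adjustment, ordering or exploratory label

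*Combined protocol and SAP*

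**What the plan says.** The Statistical Method section names the tests and the threshold for the whole trial. On tests: "Data will be analyzed using Chi square, student t-tests and Mann-Whitney U test (for non-parametric data) where appropriate". On the threshold: "A p value of <0.05 will be considered significant". Neither sentence refers to a particular outcome.

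The outcomes themselves are ranked. Specific aims separates a primary objective from secondary ones. The Primary Outcome section names a single comparison: "Number of treatment failures in the study group versus the placebo group at 3 hours post randomization". The Secondary Outcomes section then lists seven numbered items. Several hold more than one comparison, for example "Tryptase levels (Total and mature) in subjects who develop opioid-induced pruritus versus those who do not" (item 2), "Effect of age, race, and sex on the incidence of opioid-induced pruritus" (item 4) and "Effect of age, race, and sex on response to cetirizine in subjects with opioid-induced pruritus" (item 5).

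The sample size of 66 is justified on the failure rate alone. Nowhere do the documents adjust for multiple secondary tests, set an order of testing, or describe the secondary results as exploratory.

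**The concern.** Labelling an outcome secondary does not say how its p value is to be read. The one rule that does say so treats every p value alike. Followed literally, any secondary comparison with p<0.05 may be called significant, whatever the primary result.

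The exposed results are those with the least information behind them. Item 5 looks at response to cetirizine by age, race and sex. With 33 children planned per group and the assumed treatment-group failure rate of 0.3333, that is about 33 × 0.3333 = 11 failures to divide between subgroups, if the item is analysed within the cetirizine group. Age, race and sex effects are stated secondary objectives, and the plan foresees publication, so these results are likely to be reported. A reader could not tell a pre-planned claim from one of a dozen unadjusted looks.

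**Working it through.** **1. The plan's own figure.** The documents give no family-wise error rate. The only error-rate calculation is the sample size, and it concerns the primary outcome. Inputs from the Sample size calculation table: 0.6667 against 0.3333, one-sided α = 0.05, power 0.80, continuity-corrected chi-square, equal groups.

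- Uncorrected n per group = (1.645·√(2·0.5·0.5) + 0.842·√(0.6667·0.3333 + 0.3333·0.6667))² / 0.3334² = 26.7.
- Corrected n = (26.7/4)·(1 + √(1 + 4/(26.7·0.3334)))² = 32.5, rounded up to 33.

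This gives 2 × 33 = 66, as stated. The calculation uses one comparison at 0.05 and allows for no other.

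**2. Counting the secondary comparisons** (Secondary Outcomes, items 1 to 7).

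| Item | Content | Comparisons |
|---|---|---|
| 1 | "Number of drop outs in the study group versus the placebo group at the end of the study period" | 1 |
| 2 | "Tryptase levels (Total and mature) in subjects who develop opioid-induced pruritus versus those who do not" | 2 |
| 3 | "Change in Tryptase levels (Total and mature) from baseline in subjects who develop pruritus" | 2 |
| 4 | "Effect of age, race, and sex on the incidence of opioid-induced pruritus" | 3 |
| 5 | "Effect of age, race, and sex on response to cetirizine in subjects with opioid-induced pruritus" | 3 |
| 6 | Change in itch score, by group | 1 |
| 7 | Rescue doses, by group | 1 |
| | Total | 13 |

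The split follows from the methods named. Chi-square, t and Mann-Whitney tests take one factor and one measure at a time, and no multivariable model is planned that would handle age, race and sex, or both tryptase measures, together.

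Three variants matter:

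- 14, if item 6 is tested at both scoring times, 3 and 12 hours.
- 13 − 2 − 3 = 8, if items 2 and 4 cannot be run. Both need children without pruritus, whereas the inclusion criterion names children who develop it. The Study Design text can be read as enrolling some children before itching starts, so the documents leave this open.
- 7, if each numbered item is counted once.

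**3. Chance of at least one p<0.05.** Assume that every secondary null holds, each test has size exactly 0.05 and the tests are independent. Then P = 1 − 0.95^k, and the expected number of false positives is 0.05·k.

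| k | 0.95^k | P(at least one) | Expected |
|---|---|---|---|
| 7 | 0.698 | 0.302 | 0.35 |
| 8 | 0.663 | 0.337 | 0.40 |
| 13 | 0.513 | 0.487 | 0.65 |
| 14 | 0.488 | 0.512 | 0.70 |

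**4. Relaxing independence.** The documents give no correlations, so these are assumed values. They come from 400,000 simulated sets of 13 two-sided normal tests.

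- Correlation within related measures only (total with mature tryptase in items 2 and 3, itch change with rescue doses, and half that value between drop-outs and those two): at 0.5, 0.7 and 0.9, P = 0.475, 0.460 and 0.434.
- One common correlation among all 13 tests: at 0.3 and 0.5, P = 0.418 and 0.333; at 0.9, P = 0.137.

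A high common correlation is implausible, because six of the 13 tests concern age, race and sex, which have no evident reason to move together.

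**5. Relaxing the size of 0.05.** Suppose the continuity-corrected chi-square used for planning is also used for the analysis; the Statistical Method section does not say which version applies. Its exact two-sided size with 33 per group is about 0.012 at a 10% event rate and 0.027 at 33%, so binary comparisons would contribute less than step 3 assumes. Without the correction the size at those two rates is about 0.05 to 0.06.

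**The case against.** The strongest reply is that the plan already separates primary from secondary, names one primary comparison at one time, and sizes the trial on it. Unadjusted secondary p values in a small trial of this kind are a common reporting convention. This stands to the extent that the primary test's 0.05 is intact. A reader might infer from the single rule that the primary result is compromised, or that the secondary outcomes rank equally with it; the documents support neither inference.

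A reader might also infer that a one-in-two chance of a spurious finding is built into the design, with 13 tests as the minimum. That is too strong. The 0.49 needs the full count, independence, exact size and no true secondary effect. Five of the 13 tests may have no comparison group. Itch change and rescue use are tied to each other and to the primary outcome, so if cetirizine works, significance there would be a true finding.

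Nor do the documents say that a secondary result will be used to override a failed primary. The section on future research proposes a larger study, which suggests restraint.

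What these replies do not supply is a statement of how secondary p values are to be read. The convention that they are exploratory is not written down, and the rule that is written down calls every p<0.05 significant.

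**Conclusion.** The point holds in a limited form. The primary outcome keeps its 0.05. The gap is that the only significance rule extends to seven secondary outcomes without adjustment, order or label. If all secondary nulls hold, each test has size 0.05 and the tests are independent, the chance of at least one 'significant' secondary result is about 0.30 (7 tests), 0.34 (8) or 0.49 (13), and 0.51 if a 14th is run. Correlation and conservative tests pull these figures down by an amount the documents do not allow one to fix. With plausible correlation among 13 tests the chance remains well above 5%. This is a worthwhile, inexpensive correction to how results may be claimed, not a flaw in the primary analysis.

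**What to change.** In the Statistical Method section, replace the threshold sentence with: 'Significance at 0.05 is claimed only for the primary outcome; secondary outcomes are exploratory and are reported as estimates with 95% confidence intervals, and any p values shown are unadjusted for multiplicity and not used to claim significance.'

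This needs no extra patients, data or adjusted threshold. For scale, a Bonferroni threshold over 13 tests would be 0.05/13 = 0.0038, which would be hard to meet in a trial of 66. The price is that no secondary result, including the tryptase comparisons, can be called significant. If the sponsor wants one confirmatory secondary outcome, it can be named in advance and tested only if the primary is significant.

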Title: Effect of long acting antihistamine on opioid- induced pruritus: A double-blind placebo controlled study

PI: [name]

NCT #: 01825655

Unique Protocol ID: HM20003779

Document approval date: August 26, 2015

Document Type: Protocol and SAP

Protocol

Effect of long acting antihistamine on opioid- induced pruritus: A double-blind placebo controlled study.

Principal Investigator: [name]

Co-investigators: [name]

[name]

[name]

[name]

[name]

[name], PA

[name], NP

Correspondence:

[name]
Assistant Professor of Pediatrics
Division of Allergy & Immunology
Virginia Commonwealth University School of Medicine
[name]
[contact]
[contact]

Background and Significance:

Opioids are commonly used in the treatment of moderate-severe pain. Pruritus is a common adverse effect of this class of medications, occurring in up to 10% of subjects treated with oral or intravenous opioids. [1]. The prevalence goes up with the dose of opioid being used [2]. The exact mechanism for the pruritus is unknown but there are two principal theories: A peripheral effect mediated by histamine released via direct mast cell degranulation by opioids; and a central mechanism mediated by μ opioid receptors in the nervous system [3, 4].

Currently, there is no standardized treatment for opioid induced pruritus. Most studies conclude that opioid antagonists are the best treatment; however, they also decrease the analgesic effect. A recent study has compared Odansetron and diphenhydramine treatment for pruritus in women who received intrathecal opioids and found them equally effective. [5]. This study was in adults receiving intrathecal opioid. There are no pediatric studies looking at effective treatment options for opioid-induced pruritus. As a consequence, the usual practice is to discontinue the opioid and use an alternate drug for analgesia. There are no prospective double blind studies available that have looked at the effect of a second-generation, non-sedating, long- acting antihistamine on opioid induced pruritus in children.

Hypothesis:

Histamine is the primary mediator responsible for pruritus induced by oral or intravenous administration of opioids. A second generation, long acting antihistamine will be effective at relieving the pruritus and allowing continued therapy with opioids.

Specific aims:

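### Does the stated power of 0.8 at 66 patients fail because the analysis section does not repeat the one-sided, continuity-corrected test used for sizing?

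*Combined protocol and SAP*

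**What the plan says.** The Sample size calculation section states its test openly: α = 0.05, "significance level with a two group continuity corrected" chi-square, and "1 sided test, equal sample sizes in each group". Its 50% row sets failure at 0.6667 on placebo and 0.3333 on treatment, and gives 33 per group for 80% power.

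Statistical Method carries this forward as "a sample size of 66 confers a power of 0.8", again at α = 0.05. On the analysis it says "Data will be analyzed using Chi square, student t-tests and Mann-Whitney U test (for non-parametric data) where appropriate" and "A p value of <0.05 will be considered significant". It does not say whether the primary test is one- or two-sided, or whether the correction applies.

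The Primary Outcome is binary: "Number of treatment failures in the study group versus the placebo group at 3 hours post randomization". The Hypothesis is directional: "A second generation, long acting antihistamine will be effective at relieving the pruritus".

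**The concern.** A reader who meets an unqualified chi-square with a 0.05 threshold will usually expect a two-sided p-value. The sizing test is one-sided. If the analysis were two-sided and kept the correction, formula power at 66 would be about 0.70, and 0.8 would need 40 per group.

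The primary verdict can also turn on the choice. With 22/33 placebo failures against 14/33 on cetirizine, the table's test gives p = 0.042 and its two-sided version gives 0.084. A choice made after seeing the data would leave the 5% error rate unprotected. On that view, the quoted power and the stated analysis are not tied to the same test, and the plan should name one.

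**Working it through.** **Inputs.** From the table's 50% row: p1 = 0.6667, p2 = 0.3333, difference d = 1/3, mean rate 0.5, equal arms. From its heading: α = 0.05, one-sided, continuity-corrected. Power 0.8 gives z = 0.8416. The critical value is 1.6449 one-sided and 1.9600 two-sided.

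**Reproducing the 66.** The uncorrected size per group is

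m = [z_α·√(2 × 0.5 × 0.5) + z_β·√(p1(1−p1) + p2(1−p2))]² / d²

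The two square roots are 0.7071 and 0.6667. One-sided, m = (1.1631 + 0.5611)² × 9 = 26.75. The Fleiss correction is n = (m/4)·[1 + √(1 + 4/(m·d))]², which gives 32.5, rounded up to 33 per group, or 66 in total. This matches the plan. The same formula reproduces 15 of the table's 16 cells. The exception (40% reduction, 90% power) is not used by the plan.

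Two-sided, m = (1.3859 + 0.5611)² × 9 = 34.1 uncorrected, and 39.9 corrected.

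**Power at 33 per group.** The standard error is √(0.5/33) = 0.1231 under the null and √(0.4444/33) = 0.1161 under the design rates. Power is Φ[(d − c − z_α × 0.1231)/0.1161], with c = 1/33 = 0.0303 if corrected and 0 if not. Exact power comes from enumerating all binomial outcomes at 33/33.

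| Reading of the analysis | n per group for 0.8 | Argument of Φ | Formula power at 33 | Exact power at 33/33 |
|---|---|---|---|---|
| One-sided, corrected (the table's test) | 33 | 0.867 | 0.807 | 0.820 |
| One-sided, uncorrected | 27 | 1.128 | 0.870 | 0.879 |
| Two-sided, uncorrected | 35 | 0.793 | 0.786 | 0.820 |
| Two-sided, corrected | 40 | 0.532 | 0.703 | 0.746 |

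Exact power moves with arm size because the counts are discrete. At 32/32, 34/34 and 35/35 it is 0.80, 0.78 and 0.79 two-sided uncorrected, and 0.72, 0.71 and 0.72 two-sided corrected. If all 73 recruits were evaluable (36/37), two-sided corrected power would be 0.76 by formula and 0.79 exact.

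**The example, 22/33 v 14/33.** The pooled rate is 36/66 and the standard error 0.1226. Uncorrected, z = (8/33)/0.1226 = 1.978, two-sided p = 0.048. Corrected, z = (7/33)/0.1226 = 1.730, p = 0.042 one-sided and 0.084 two-sided. Three of the four readings are therefore significant, since one-sided uncorrected is half of 0.048.

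**How often verdicts differ under the design rates.** The table's test and the two-sided uncorrected test almost never disagree in favour of cetirizine at 33/33. With 16 to 27 placebo failures, both need a difference of 8. They disagree in 2.9% of trials at 32/34 and 5.5% at 34/34. The table's test and its two-sided corrected version disagree in 7.5% at 33/33 (0.820 − 0.746, from unrounded values), 9.8% at 32/34 and 12.7% at 34/34.

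**The case for a change.** The best case for a change is that the table heading describes how the numbers were computed, not how the data will be analysed. The corrected chi-square is the only version the documents describe, so an analyst might keep it and report a two-sided p-value out of habit. Power would then be 0.70 to 0.75, the verdict would differ from the table's test in roughly one trial in 8 to 13, and one sentence would close the gap.

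Part of this stands. Statistical Method is silent on both features, and the two-sided corrected reading does lose material power.

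The argument is selective, however. Sidedness and correction stand in the same heading, so if that heading is evidence for the correction it is equally evidence for a one-sided test. Carried over whole, it gives the plan's 66 and 0.8. Set aside whole, in favour of an ordinary two-sided uncorrected chi-square, it leaves power at 0.79 by formula and 0.82 exact. Only half of it, taken without the other half, produces the shortfall.

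Nor does the remedy point to a particular correction. Restating the table's test changes nothing, two-sided uncorrected moves 0.80 to 0.79, and two-sided corrected is a debatable preference. Each has its price: exact error at 33/33 with a common failure rate of 0.5 is 0.032 for the table's test, 0.036 for two-sided corrected and 0.064 for two-sided uncorrected.

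**Conclusion.** The concern does not call for a change. The 66 is correct for the test the plan discloses, no sentence contradicts that test, and the directional hypothesis is compatible with it. What remains is an analysis section that does not repeat two details given elsewhere in the same document, a gap that an analyst can fill sensibly from the table heading or with an ordinary chi-square.

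The size of the matter is formula power between 0.70 and 0.87 at 66 evaluable patients. Three readings lie at 0.79 or above, and one falls about 10 points short (about 5 by exact calculation at 33/33). All these figures assume the table's failure rates. The 0.3333 matches the plan's experience in only 6 patients, so a difference of one point in nominal power carries little weight. Stating the sidedness and correction when results are reported would be good practice, but its absence here makes no stated figure wrong.
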